2 INTRODUCTION

2.1 Study Rationale

Patients undergoing treatment with durvalumab for unresectable Stage III non-small cell lung cancer (NSCLC) after 2 or more cycles of concurrent platinum-based chemotherapy and radiation therapy (concurrent chemoradiotherapy [cCRT]) can experience pulmonary adverse events (AEs) that lead to treatment discontinuation and morbidity. This study, ON TRAX, is a pilot study to evaluate the potential benefit of multiparametric mobile applications and connected medical devices in collecting data to facilitate or improve early identification of pulmonary AEs in patients with unresectable Stage III NSCLC receiving durvalumab treatment. The outcomes of this study will determine whether this multiparametric mobile technology will be progressed to a fully powered study for the early detection of pneumonitis and pulmonary AEs in patients with unresectable Stage III NSCLC.

This project seeks to understand if the multiparametric mobile technology devices integrate well into a patient's daily life with minimal burden and to collect vital signs and respiratory data. These devices can then track and detect changes in a patient's vital signs and respiratory function and aid physicians in detection of pulmonary AEs.

2.2 Background

The PACIFIC study was a randomized, placebo-controlled, Phase 3 trial evaluating the immune checkpoint inhibitor durvalumab in patients with unresectable Stage III NSCLC who did not have disease progression after 2 or more concurrent cycles of platinum-based chemoradiotherapy. At the first planned interim analysis, the trial showed that durvalumab treatment significantly prolonged progression-free survival, as compared with placebo, with median durations of 16.8 months (95% confidence interval [CI], 13.0 to 18.1 months) and 5.6 months (95% CI, 4.6 to 7.8 months), respectively ([Antonia et al. 2017](#)). On the basis of these results, durvalumab treatment was approved by the United States Food and Drug Administration (US FDA) for the treatment of unresectable Stage III NSCLC in patients whose disease had not progressed after platinum-based chemoradiotherapy. In addition, overall survival was found to be significantly prolonged in durvalumab-treated patients compared with the placebo group (stratified hazard ratio for death, 0.68; 99.7% CI, 0.47 to 0.997; $p=0.0025$) ([Antonia et al. 2018](#)). During the PACIFIC trial, pneumonitis or radiation pneumonitis of any grade occurred in 33.9% and 24.8% and Grade 3 or 4 pneumonitis or radiation pneumonitis occurred in 3.4% and 2.6% of durvalumab and placebo patients, respectively ([Antonia et al. 2017](#)). A total of 15.4% of patients in the durvalumab arm discontinued study drug due to AEs, compared with 9.8% in the placebo arm ([Antonia et al. 2018](#)). The most frequent AEs leading to study drug discontinuation were pneumonitis (4.8% in the durvalumab group and 2.6% in the placebo group), radiation pneumonitis (1.3% in both groups), and pneumonia (1.1% in the durvalumab group and 1.3% in the placebo group). Immune checkpoint-inhibitor-related pneumonitis is a potentially serious and life-threatening toxicity. The reported incidence of pneumonitis in studies investigating anti-programmed cell death 1/programmed cell death-ligand 1 is variable and ranges from 0% to 10%, with an overall incidence of 2.7% reported in a recent meta-analysis of 20 studies with programmed cell death 1 (PD-1) inhibition; the incidence in patients with lung cancer as the underlying diagnosis is even higher ([Nishino et al. 2016](#)).

The development of new multiparametric healthcare technologies has provided new sources of data collection for healthcare providers. This new form of data collection may improve healthcare delivery and outcomes. Given the potential impact of these new technologies, it is important to understand the utility of multiparametric mobile technology for patients and how information collected through these can be used to improve patient care. By analyzing disease characteristics and health status alongside a specific patient's history, it may be possible to predict changes in organ function and intervene earlier with the appropriate medical care. Previous studies have documented the ability of home spirometry devices to detect pulmonary AEs in lung transplant patients, establishing proof of principle in lung transplant and NSCLC populations (Finkelstein et al. 1999; Finkelstein et al. 2013; Wang et al. 2013; Torre-Bouscoulet et al. 2018; Basch et al. 2017).

Multiparametric mobile technology devices and applications are non-invasive and simple to use, automatically collecting data from patients and/or allowing patients to report data in almost any location, whenever convenient. Multiparametric mobile technology has been used in previous studies (QUASAR 2; Cloudy with a Chance of Pain Study), where large volumes of data were quickly and efficiently entered by a high proportion of patients who expressed their satisfaction with the technology.

2.3 Benefit/Risk Assessment

All patients who participate in this study will receive standard of care appropriate for their lung cancer as determined by their treating physician.

The technology to be used in this study is non-invasive and has been used previously in other settings, including clinical studies; it is believed to pose an extremely low risk to study patients. Patients using the wearable arm device have reported minor events of skin irritation and discomfort during sleeping. In addition, patients undergoing concomitant anti-coagulation therapy have experienced ecchymosis near the device site. As part of their standard of care, patients will undergo routine assessment by their physician, who will decide when regular visits should take place. Due to the nature of the technology used and the fact that all other procedures are standard of care, study-related or multiparametric mobile technology-related AEs are expected to be rare. The study sponsor, AstraZeneca (AZ), has concluded that this study has a favorable benefit/risk ratio.

Data from this pilot study will be used by AZ to decide whether a larger comparative study of patients with and without the technology is warranted, which will potentially benefit other patients in the future.

3 OBJECTIVES AND ENDPOINTS

[figure not shown]
3.1 Study Objectives

The primary objective of the study is to describe the identification of treatment-emergent pneumonitis by grade (regardless of radiation therapy and/or immune-related etiology) in patients with unresectable Stage III NSCLC receiving durvalumab through the use of mobile technology which collects patient reported outcomes (PROs), vital signs (temperature, heart rate, respiratory rate), oxygen saturation (pulse oximetry), pulmonary function tests (spirometry), and physical movement (number of steps per day).

The secondary objectives are:

- To describe durvalumab treatment discontinuation due to pulmonary AEs, including pneumonitis
- To describe the duration of durvalumab use
- To describe the incidence of pulmonary AEs by grade
- To describe the severity of pulmonary AEs (including pneumonitis) and use of medication to manage AEs
- To describe the time to development of Grade 3 to 5 AEs, including pneumonitis
- To describe health-related quality of life (QoL) during the study and its relationship with AEs

The exploratory objectives are:

3.2 Study Endpoints

The endpoint used to address the primary objective is:

- Occurrence of pneumonitis (either radiation or immune-mediated, by grade).
 - Grade of pneumonitis at diagnosis and highest grade of pneumonitis

The endpoints used to address the secondary objectives are:

- Occurrence of pulmonary AEs, including diagnoses of events, by grade
- Duration (days) of pulmonary AEs by type and grade
- Permanent discontinuation of durvalumab due to pulmonary AEs, including pneumonitis
- Early discontinuation of durvalumab treatment for any reason
- Duration (days) of durvalumab treatment
- Treatment interruptions, duration (days) of interruptions, and the reason for interruptions that will be captured in a standard data management form with the site physician documenting reasons in patient charts
- Time (days) to development of Grade 3 to 5 AEs, including pneumonitis

- Prescription of medication used to manage pulmonary AEs and duration (days) of treatment
- Change in QoL scores from baseline

The endpoints used to address the exploratory objectives are:

CCI

4 METHODOLOGY

4.1 Study Design

[figure not shown]
This is a multicenter, prospective, interventional pilot study conducted in the United States that will include patients with unresectable Stage III NSCLC whose disease has not progressed following 2 or more cycles of cCRT, and who will be treated with durvalumab for up to 12 months or until confirmed disease progression, permanent discontinuation of durvalumab, the initiation of alternative cancer therapy, unacceptable toxic events, death, or withdrawal of consent, whichever is sooner.

Patients will be enrolled after their treating physician has prescribed durvalumab and before they start durvalumab treatment. Patients will receive mobile and wearable devices alongside their durvalumab treatment without any additional interventions. Patients will receive training on the mobile applications and supportive devices. Patients will return to their study site for routine visits and durvalumab infusions as guided by their physician over the duration of the study.

All patients will receive routine medical care as determined by their physician and will be instructed to contact the site with any new or worsening symptoms including, but not limited to: trouble breathing, chest pain, new or worsening cough, productive cough with purulent secretions, shortness of breath, fever, or tachycardia.

An overview of the study design is presented in [Figure 1](#).

Figure 1 Study Design

4.1.1 Data Sources

Data will be collected prospectively using an integrated approach, where data from existing medical records will be combined with data collected via multiparametric mobile technology, called the Current Wearable Health Monitoring System.

Patients will complete QoL assessments via a tablet application at baseline on Day 1, once every 2 weeks for the first 3 months of the study followed by once per month thereafter, and at their End-of-Study visit.

CCI

4.2 Scientific Rationale for Study Design

The primary objective of the study is to describe the identification of treatment-emergent pneumonitis by grade in patients with unresectable Stage III NSCLC receiving durvalumab through the use of mobile technology which collects PROs, vital signs (temperature, heart rate, respiratory rate), spirometry (i.e., pulmonary function), pulse oximetry (i.e., oxygen saturation), and physical movement (number of steps per day). The multiparametric mobile technology being evaluated in this study does not involve administration of any medicinal product (other than durvalumab) or similar entity. Consequently, this study does not seek to evaluate any parameters related to dose, method of administration, or mode of action of any treatment patients receive per standard of care.

This is a descriptive pilot study with a sample size of 75 patients. The contributions of PRO variables and other variables collected via the Current Wearable Health Monitoring System to the identification of pneumonitis will be assessed using a logistic regression; addressing the question of whether there is an association between a pneumonitis event and variables collected prior to the event. Analyses of all secondary and exploratory endpoints will be descriptive only. Since this is a pilot study, a holistic multifaceted approach will be used to ascertain success and determine subsequent studies.

The decision to move from the pilot study to a larger trial will be determined using a number of factors. The study team will look to see a numerical trend in the primary endpoint as well as positive findings for the secondary and exploratory endpoints. Additional critical success factors are as follows:

- Treating physicians find the mobile technology to be useful/effective in the early detection of pneumonitis, and
- Patients are willing and able to effectively wear and use the devices for the full course of durvalumab.

An execution of retrospective clinical chart reviews of PACIFIC patients to evaluate/compare to real world pneumonitis data versus PACIFIC may also be considered to provide additional context before moving to a fully powered 2-armed trial. Also, supporting publications and to-be-published scientific literature of similar single-armed pilot studies will be used to guide

decision making to move to a larger trial. Additional details will be found in the statistical analysis plan (SAP).

5 STUDY POPULATION

The population will be comprised of 75 patients with unresectable Stage III NSCLC whose disease has not progressed following 2 or more cycles of cCRT, and who are eligible to receive durvalumab, as outlined in the package insert. Patients will be recruited in up to 30 sites.

Each patient should meet all of the inclusion criteria and none of the exclusion criteria for this study.

Prospective approval of protocol deviations to recruitment and enrollment criteria, also known as protocol waivers or exemptions, are not permitted.

5.1 Inclusion Criteria

Patients are eligible to be included in the study only if all of the following inclusion criteria apply:

1. Patient able to provide written signed informed consent prior to any study-specific procedures.
2. Patient must be ≥ 18 years except in the state of Alabama where the legal age is 19 years.
3. Patient has unresectable Stage III NSCLC that has not progressed following concurrent platinum-based chemotherapy and radiation therapy and is eligible to receive durvalumab according to the US FDA approved package insert.
4. Patient will initiate durvalumab treatment within 2 weeks of Baseline and receive at least 1 dose of durvalumab.
5. Patient is able and willing to use the mobile application and connected devices on a daily basis for up to 12 months.
6. Patient is able to complete QoL assessments once every 2 weeks for the first 3 months of the study and monthly thereafter.

5.2 Exclusion Criteria

Patients meeting any of the following criteria will be excluded from the study:

1. Patient is currently enrolled in an interventional research study or clinical trial.
2. Patient is currently oxygen dependent.
4. Patient has comorbidities that will prevent consistent and reliable measurement assessments with multiparametric mobile technology including severe chronic obstructive pulmonary disorder (COPD) (defined as patients who, according to the Global Initiative for Chronic Obstructive Lung Disease [GOLD] 2019 guidelines, have severe and very severe airflow limitation due to COPD; these are patients with forced expiratory volume/forced vital capacity [FEV₁/FVC] < 0.70 and FEV₁ $< 50\%$ predicted), severe asthma, congestive heart failure [CHF], interstitial lung disease [ILD], and others).
5. Patients on other immunotherapy or systemic immunosuppressants other than durvalumab.
6. Patients with active or prior autoimmune disease or history of immunodeficiency, any unresolved toxicity Common Terminology Criteria for Adverse Events (CTCAE)

- > Grade 2 from the prior cCRT and patients with medical conditions that required systemic immunosuppression.
- 7. In the opinion of the site physician, if the patient is unlikely to be able to complete the 12-month study period due to reasons that may include, but are not limited to, the following: difficulties with mobile literacy, unwillingness/inability to use devices or interact with an application, or treatment compliance.
- 8. For women only – currently pregnant.

5.3 Discontinuation and Withdrawal of Patients

As a patient's participation is voluntary, patients are free to discontinue their participation in this study at any time and without prejudice to his/her subsequent medical treatment. Patients who wish to discontinue must notify their study physician. Patients who discontinue should be asked about the reason(s) for their discontinuation, and this will be noted in the patient study records and the Data Capture Portal by the study site.

A patient can be withdrawn from the study at the discretion of the site physician if they do not comply with study requirements. Patients who choose to withdraw or are withdrawn by the site physician may be replaced, at the discretion of AZ, by enrolling additional patients beyond the goal of 75.

If a patient is withdrawn prior to completing the study, any known reason for withdrawal should be documented by the study site (e.g., safety reason, change of address, death, voluntarily withdrawal, non-compliance). All information already collected as part of the study will be retained for analysis. The patient will be asked if information pertaining to the End-of-Study visit and Safety Follow-up visit can be collected from his/her medical records. The patient will also be asked to complete the final QoL and CCI [REDACTED] at the End-of-Study visit. However, no further efforts will be made to obtain or record additional information regarding the patient. The patient and sites will be provided instructions on how to return study equipment as required.

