7.1.2 Study Period

All patients enrolled will be followed up to 12 months on durvalumab or until confirmed disease progression, permanent discontinuation of durvalumab treatment, the initiation of alternative cancer therapy, unacceptable toxic events, death, or withdrawal of consent, whichever is sooner.

At the End-of-Study visit (after 12 months of durvalumab dosing or upon withdrawal/discontinuation), information about the patient including height, weight, vital signs (temperature, heart rate, respiratory rate, and blood pressure), oxygen saturation, pulmonary-related concomitant medications and procedures, and information on AEs/SAEs (including pneumonitis), will be collected. The patient will also be prompted to take the QoL and **CCI**

A patient is considered to have completed the study when he/she has provided multiparametric data using the devices and installed application on a tablet in the Current Wearable Health Monitoring System through 12 months (or 26 cycles) of durvalumab treatment. In certain cases, a patient who does not complete all 26 cycles (i.e., durvalumab treatment prematurely discontinued due to an immune-related AE) may still be considered a study completer.

The end of study is defined as the date the last expected data will be collected.

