8.3.1.3 Adverse Events Information

AE and SAE collection will occur at Baseline (i.e., after the patient signs the ICF), during standard of care visits, at the End-of-Study visit, and for 30 days after the End-of-Study visit. The following information should be collected for AEs and SAEs reported to AZ or its delegate, Syneos Health Pharmacovigilance:

- AE (verbatim)
- The date (and time) when the AE started and stopped
- Intensity rating scale (intensity, maximum intensity or changes in intensity)
 - Mild
 - Moderate

- Severe

It is important to distinguish between serious and severe AEs. Severity is a measure of intensity whereas seriousness is defined by the criteria in [Section 8.3.1.1](#). An AE of severe intensity need not necessarily be considered serious. For example, nausea that persists for several hours may be considered severe nausea, but not an SAE unless it meets the criteria shown in [Section 8.3.1.1](#). On the other hand, a stroke that results in only a limited degree of disability may be considered a mild stroke but would be an SAE when it satisfies the criteria shown in [Section 8.3.1.1](#). The severity (i.e., grade) of all AEs will be documented at Baseline, during standard of care visits, and through final resolution (or other final outcome). When possible, the severity of Baseline conditions (i.e., AE-related signs/symptoms, laboratory measurements) will also be documented.

- Whether AE is serious or not
- Physician causality against durvalumab
- Action taken with regard to durvalumab
- Outcome

In addition, the following variables should be collected for SAEs reported to AZ (or its delegate, Syneos Health Pharmacovigilance, as described in [Sections 8.3.1.4](#) and [8.3.1.5](#), as applicable):

- Date site physician became aware of SAE
- Date AE met criteria for SAE
- The reason AE is serious
- Date of hospitalization
- Date of discharge
- Date of death
- Autopsy performed

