2. ANALYSIS SETS

2.1 Definition of Analysis Sets

2.1.1 Safety Analysis Set

The Safety Analysis Set (SAF) will include all enrolled patients who take at least 1 dose of durvalumab.

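### A patient withdrawn by the site for non-compliance while still on durvalumab can have new pneumonitis that is never recorded once the 30-day safety follow-up has passed

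*Protocol*

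**What the plan says.** **Withdrawal.** Protocol 5.3 states: "A patient can be withdrawn from the study at the discretion of the site physician if they do not comply with study requirements". The requirements are not itemised there, but inclusion criterion 5 in Section 5.1 reads: "Patient is able and willing to use the mobile application and connected devices on a daily basis for up to 12 months". After withdrawal, "The patient will be asked if information pertaining to the End-of-Study visit and Safety Follow-up visit can be collected from his/her medical records", and the patient is asked to complete the final questionnaires. The section then closes off anything more: "However, no further efforts will be made to obtain or record additional information regarding the patient".

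**Follow-up.** Protocol 7.1.2 states: "All patients enrolled will be followed up to 12 months on durvalumab or until confirmed disease progression", and goes on to name stopping durvalumab for good, a new cancer therapy, toxicity, death and withdrawn consent. The synopsis, Protocol 4.1 and SAP 1.2 carry the same list. Withdrawal by the site for non-compliance is not on it, although the next paragraph of 7.1.2 holds the End-of-Study visit "after 12 months of durvalumab dosing or upon withdrawal/discontinuation". Under Protocol 8.3.1.3, AEs are collected at Baseline and then "during standard of care visits, at the End-of-Study visit, and for 30 days after the End-of-Study visit". Table 1 schedules durvalumab data only as far as the End-of-Study visit.

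**Analysis.** SAP 2.1.1 states: "The Safety Analysis Set (SAF) will include all enrolled patients who take at least 1 dose of durvalumab". SAP 6 drops the full analysis set. SAP 4.2.1 takes pneumonitis from the CRF and, if there are enough events, gives a percentage of patients by grade with a 95% CI; otherwise it gives a listing. SAP 4.2.2.5 cuts durvalumab duration at study exit when treatment is still running. SAP 4.2.2.7 censors time to Grade 3 to 5 events at study exit. SAP 4.2.4.8 runs the treatment-emergent window to 30 days after the last durvalumab dose, whereas Protocol 8.3.1.1 ends it at the End-of-Study visit.

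**The concern.** Pneumonitis, pulmonary AEs and durvalumab dates come from the CRF and the medical record. None of them needs the wearable or the spirometer. A patient who stops using the devices but stays on durvalumab remains at risk and, in principle, observable. Section 5.3 nevertheless allows that patient to leave the study altogether, after which new events are not sought.

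What is at stake is the primary endpoint, occurrence and highest grade of pneumonitis, together with the endpoints on durvalumab discontinuation and duration. An unrecorded event in a patient who stays in the denominator pulls the percentage down, and the exact confidence interval does not reflect it. Protocol 4.2 says that the sponsor will look for a numerical trend in the primary endpoint when deciding on a larger trial, and that a comparison with chart-review data from the cited Phase 3 trial may be considered.

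**Working it through.** **1. Trace one patient.** Take a patient dosed on Day 1, withdrawn by the site for non-compliance at month 3, and treated with durvalumab until month 12.

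- Protocol 7.1.2: withdrawal triggers the End-of-Study visit, at about month 3.
- Protocol 5.3, 8.3.1.3 and Table 1: with the patient's agreement, AEs are captured for 30 more days, to about month 4. Without it, capture ends earlier.
- From month 4 to month 12, new pneumonitis or a durvalumab stop is not sought.
- SAP 4.2.4.8: the treatment-emergent window for this patient runs to 30 days after the last dose, about month 13. Section 5.3 leaves most of it unfilled.
- SAP 2.1.1: the patient stays in the safety analysis set. SAP 4.2.1 would most likely count the patient as event-free.
- SAP 4.2.2.5: treatment duration is entered as about 3 months and summarised with ordinary statistics, without censoring.
- SAP 4.2.4.1: a later durvalumab discontinuation is absent from the numerator, while all enrolled patients form the denominator.
- SAP 4.2.2.7: only time to Grade 3 to 5 events censors the patient at exit.

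**2. The plan's own figure.** Protocol 9.1, Table 4, gives an upper limit of 4.8% for 0 of 75. It reproduces: 1 − 0.025^(1/75) = 4.8%. All 12 rows match the exact two-sided interval. The table assumes that all 75 patients are observed throughout. If only 60 were, and the rest added nothing, the limit would be 1 − 0.025^(1/60) = 6.0%.

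**3. Size of the loss, as an illustration.** Inputs:

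- p = 33.9%, the any-grade rate in the durvalumab arm of the Phase 3 trial (Protocol 2.2). The protocol does not give a time horizon; 12 months is an assumption.
- N = 75 (Protocol 9.1).
- Assumed: constant hazard, withdrawal at 3 months unrelated to risk, 30 days of follow-up obtained, so observation to day 120. The withdrawn fraction w is not in the documents; 10% to 30% is shown.

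Hazard: λ = −ln(1 − 0.339) = 0.414 per year.

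Risk by day 120: 1 − exp(−0.414 × 120/365) = 12.7%.

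Observed percentage = (1 − w) × 33.9% + w × 12.7%. Missed cases = 75 × (33.9% − observed) = 75 × w × 21.2%.

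| w | Observed | Missed of 75 |
|---|---|---|
| 10% | 30.51 + 1.27 = 31.8% | 1.6 |
| 20% | 27.12 + 2.54 = 29.7% | 3.2 |
| 30% | 23.73 + 3.81 = 27.5% | 4.8 |

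**4. Sensitivity.**

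- Withdrawal at month 2, 5 to 20 patients: 32.3% to 27.5% with the 30-day follow-up, 32.1% to 26.6% without it.
- Withdrawal at month 6 with the 30-day follow-up, 5 to 20 patients: 33.1% to 30.6%.
- All risk in the first 6 months: λ = 0.414/6 = 0.069 per month, and risk by month 4 is 1 − exp(−0.276) = 24.1%. With 20% withdrawn at month 3, observed = 27.12 + 4.82 = 31.9%, instead of 29.7%. For withdrawal at month 6 the loss is zero.

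**5. Against sampling error.** At 21 of 75 (28.0%, close to the 30% row), the exact 95% CI is 18.2% to 39.6%, which contains 33.9%.

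**The case against.** The case on the other side is substantial, and several parts of it stand.

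- A reader might infer that AE collection ends at withdrawal. It does not. With the patient's agreement, the End-of-Study and 30-day information is still collected.
- Pneumonitis already present at exit has a route to capture. Protocol 8.3.1.3 documents severity through final resolution, and 8.3.1.4 and 8.3.1.5 leave follow-up of unresolved AEs and SAEs to a documented investigator decision. The clear gap is new onset after the 30 days, or earlier if record access is refused.
- Section 5.3 does not say that stopping the devices leads to withdrawal. It is permissive and speaks of study requirements. Device use is a reasonable reading, not a stated rule.
- SAP 4.2.1 names no denominator and excludes some patients with ongoing baseline conditions. The safety set is the likely basis because no other is defined. If events are few, there is a listing and no percentage, though a listing would miss the same cases.
- Section 7.1.2 does provide for an End-of-Study visit at withdrawal, so the mismatch with 5.3 is an omission from a list and not a flat contradiction.
- It might be said that patients who feel worse stop first, so the true loss is larger. That direction is not settled: if symptoms drive the stopping, pneumonitis may surface within the 30 days and be captured.

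One argument does not carry. The primary objective concerns identification through mobile technology, so pneumonitis long after device use ended might seem irrelevant. But the primary endpoint (SAP 3.3) and primary analysis (SAP 4.2.1 and 6) are occurrence of pneumonitis by grade, with no link to device use.

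**Conclusion.** The concern holds in a narrow form. A site-withdrawn patient who stays on durvalumab can have new pneumonitis, or a later durvalumab discontinuation, that is never recorded. The crude percentage and the durvalumab-duration summary make no allowance for this. Section 5.3 is not aligned with the end points in 7.1.2 or with the SAP's treatment-emergent window.

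Missed events act in one direction only, but the size is unknown, because the documents give neither a non-compliance rate nor the timing of onset. The 1.6 to 4.8 missed cases of 75 rest on the assumed 12-month horizon, constant hazard, month-3 withdrawal unrelated to risk, and 30-day follow-up obtained. The loss lies within sampling error and can be zero if onset is early. A reader might infer that the primary result is materially distorted; the documents do not support that. This is a cheap improvement to a descriptive pilot, not a flaw that invalidates it.

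**What to change.** 1. In Protocol 5.3, separate stopping device and tablet tasks from leaving the study.
2. For patients who stop device use, continue to take AEs (including pneumonitis dates and grade), pulmonary medication and durvalumab dates from medical records, with consent, until a Section 7.1.2 end point plus 30 days. End record review only when the patient withdraws consent to it.
3. Record the device-stop date as its own item. SAP 4.2.4.1 already tabulates treatment and study discontinuation separately, so this is one added line.
4. In SAP 4.2.1, name the analysis set, and report a cumulative incidence of pneumonitis censored at last AE contact beside the crude percentage.
5. Reconcile the treatment-emergent window in Protocol 8.3.1.1 with SAP 4.2.4.8.

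The cost is wording in 5.3 and the consent form, and continued chart abstraction into the existing database for the affected patients. No visits or procedures are added. The consent text was not among the pages available, so how much of it must change cannot be judged here.
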